^c For subjects who complete the study at week 18, the visit includes all required safety follow-up data collection. All subjects who terminate the study early (ie, prior to completing the week 18 visit), will complete an Early Termination visit consisting of all assessments included in the week 12, day 85 pre-dose visit. In addition, a safety follow-up visit will occur 6 weeks (± 3 days) after the last dose of investigational product to collect all required safety data including adverse events, serious adverse events, disease related events, concomitant therapies, safety labs/assessments, anti-AMG 592 antibody, and urine pregnancy test.
^d For women of childbearing potential, serum pregnancy test is required at screening. All other pregnancy tests are urine. Positive urine pregnancy test should be confirmed with serum pregnancy test.

^e Either a PPD or Quantiferon test will be done during screening.

^f All clinical laboratory (ie, chemistry, hematology) and pre-dose blood samples must be collected prior to administration of investigational product. Pharmacokinetic (PK), pharmacodynamic and antibody blood samples may not be drawn through a central or peripheral line. PK samples should be collected at the exact nominal time point as noted. If unable to collect a PK sample at the specified nominal time point collect it as close as possible to the nominal time point and record the actual collection time. PK samples not collected at exact nominal time point will not be considered protocol deviations.

^g Can be done as a part of the clinical chemistry.

^h DNA will be extracted only in subjects who provide additional consent for pharmacogenetics testing.

Approved

[figure not shown]
Table 2-2. Phase 1b Schedule of Activities Follow-up

| Study week | Follow-up | | | |
|--|-----------|----|-----|--------------------------|
| | 13 | 14 | 16 | 18/SFU ^a /EOS |
| Study day | 92 | 99 | 113 | 127 |
| GENERAL AND SAFETY ASSESSMENTS | | | | |
| Weight | | | | X |
| Vital signs | X | X | X | X |
| Adverse events | X | X | X | X ^a |
| Serious adverse events | X | X | X | X ^a |
| Disease-related events | X | X | X | X ^a |
| Concomitant therapies review | X | X | X | X ^a |
| LABORATORY ASSESSMENTS | | | | |
| Urine pregnancy test | | | | X ^a |
| CRP and ESR | | | | X ^a |
| Hematology | | X | X | X ^a |
| Chemistry | | | | X ^a |
| PBMC | | | | X ^a |
| PHARMACOKINETICS AND ANTIBODIES | | | | |
| Pharmacokinetic samples | X | X | X | X |

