9.2.3.2 Vital Signs

The following measurements must be performed: systolic/diastolic blood pressure, heart rate, respiratory rate, and temperature. Subject must be in a supine position in a rested and calm state for at least 5 minutes before blood pressure assessments are conducted. If the subject is unable to be in the supine position, the subject should be in most recumbent position as possible. The position selected for a subject should be the same that is used throughout the study and documented on the vital sign CRF. The temperature location selected for a subject should be the same that is used throughout the study and documented on the vital signs CRF. Record all measurements on the vital signs CRF.

Approved

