2.1 Objectives and Endpoints

Objectives	Endpoints
Primary	
Phase 1b 
To evaluate the safety and tolerability of subcutaneous (SC) dose administrations of AMG 592 in subjects with active rheumatoid arthritis (RA)	Phase 1b 
Treatment-emergent adverse events.Clinically significant changes in vital signs, laboratory safety tests, and electrocardiograms (ECGs)
Phase 2a 
To evaluate the efficacy of AMG 592 at week 12 as measured by the American College of Rheumatology 20% improvement criteria (ACR 20) in adult subjects with moderate to severe RA	Phase 2a 
ACR 20 at week 12
Secondary	
Phase 1b 
To characterize the pharmacokinetic (PK) profile following treatment with AMG 592	Phase 1b 
AMG 592 serum concentration and PK parameters including, but not limited to, maximum observed concentration (C_{max}), the time of maximum observed concentration (T_{max}), and area under the concentration-time curve (AUC_{tau}) after the first and last doses.
Phase 1b 
To evaluate the incidence of anti-AMG 592 antibody formation and cross-reactivity to human IL-2.	
Anti-AMG 592 antibodies and cross-reactivity to IL-2.Anti-AMG 592 and anti-IL-2 neutralizing antibodies

Objectives	Endpoints

Phase 2a
To evaluate the effect of treatment with AMG 592 on other measures of disease activity at week 12	
Phase 2a
ACR 50/70 at week 12Disease activity score (28 joints) calculated using the erythrocyte sedimentation rate formula (DAS28-ESR) and change from baseline at week 12Disease activity score (28 joints) calculated using the C-reactive protein formula (DAS-28-CRP) and change from baseline at week 12

To evaluate the safety of AMG 592	
Treatment-emergent adverse events.Clinically significant changes in vital signs, laboratory safety tests

To characterize the PK of AMG 592 in subjects with RA	
AMG 592 serum concentration and PK parameters

Exploratory

Objectives	Endpoints

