9.1 General Considerations

Analyses of phase 1b data will be provided separately than analyses of phase 2 data. Descriptive statistics will be provided for selected demographics, safety, PK, PD, and biomarker data. Descriptive statistics on continuous measurements will include means, medians, standard deviations, and ranges, while categorical data will be summarized using frequency counts and percentages. Data will be presented and summarized by treatment and by time as appropriate. **Data collected at unscheduled visits or timepoints will be included in the analysis unless stated otherwise.**

Only critical subject-level data listings will be provided in the Clinical Study Report. Additional listings of subject-level data will be reviewed as part of DLRMs or ongoing data review for assessment of product's safety, efficacy and the quality of data, but will not be included in the Clinical Study Report.

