9.6 Safety Analyses

9.6.1 Analyses of Primary Safety Endpoint(s)

Phase 1b

The primary endpoint for phase 1b is safety. The analysis will include the descriptive summary statistics for adverse events, disease-related events, laboratory measures, vital signs, physical measurements and ECG. Details are described in respective section below.

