9.6.4 Vital Signs

Phase 1b

The analyses of vital signs will include summary statistics at selected time points, **post-baseline maximum/minimum and change from baseline to post-baseline maximum/minimum** by treatment group for systolic/diastolic blood pressure, heart rate and temperature.

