9.6.5 Physical Measurements

Phase 1b

The analyses of physical measurements will include summary statistics **of weight at scheduled time points** by treatment group.

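### SAP 9.6.4 leaves respiratory rate out of the phase 1b vital-sign summaries, although the protocol requires it to be measured (minor)

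*SAP*

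**What the plan says.** The protocol's assessment section is mandatory and lists what is measured: "The following measurements must be performed: systolic/diastolic blood pressure, heart rate, respiratory rate, and temperature". It continues: "Record all measurements on the vital signs CRF". The phase 1b follow-up schedule (Protocol Table 2-2) has a single vital-signs row, "Vital signs | X | X | X | X", marked at all four follow-up visits. It is not split by parameter.

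Vital signs belong to the phase 1b primary endpoint, which SAP 2.1 words as "Clinically significant changes in vital signs, laboratory safety tests, and electrocardiograms (ECGs"). SAP 9.6.1 says how that endpoint will be analysed: "The analysis will include the descriptive summary statistics for adverse events, disease-related events, laboratory measures, vital signs, physical measurements and ECG". It leaves the detail to the section for each measure.

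For vital signs that section is SAP 9.6.4. It plans three kinds of summary: statistics at chosen time points, the highest and lowest post-baseline values, and the change from baseline to those extremes. These are to be given "by treatment group for systolic/diastolic blood pressure, heart rate and temperature". Protocol 10.3.2.3.4, the corresponding analysis section, speaks of vital signs in general and names no parameters.

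**The concern.** The SAP is the document the tables are programmed from. SAP 9.6.1 passes the detail of the primary safety analysis to 9.6.4, and 9.6.4 gives an explicit list, so that list settles which vital signs are described by treatment group. Respiratory rate is the only measurement required by Protocol 9.2.3.2 that is not on it.

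The visible text does not show whether this was a decision or an oversight. SAP Section 10, which records departures from the protocol, covers only the dropped ECG listing. The Appendix F entry for 9.6.4 repeats the same four parameters and does not comment on the missing one.

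What is at stake is completeness. In a part of the study whose primary purpose is safety, the planned tables would describe four of the five measured vital signs by group, and the reader would not know why the fifth is absent.

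**Working it through.** No sample-size, power or error-rate figure is involved. The check compares two lists and then searches for an explanation.

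**Step 1: compare the lists.**

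| Parameter | Protocol 9.2.3.2 (measure and record) | SAP 9.6.4 (summarise) |
|---|---|---|
| Systolic blood pressure | yes | yes |
| Diastolic blood pressure | yes | yes |
| Heart rate | yes | yes |
| Respiratory rate | yes | **no** |
| Temperature | yes | yes |

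Required: 5. Named: 4. Missing: 5 − 4 = 1, and 1/5 = 20%. If blood pressure is counted as one item, it is 1 of 4.

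**Step 2: express this in planned output.** With three kinds of summary per parameter, full coverage is 3 × 5 = 15 items. The SAP plans 3 × 4 = 12, so 15 − 12 = 3 are absent. This is the same 4-in-5 ratio scaled up. It shows the size of the programming change and adds no weight to the point.

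**Step 3: look for respiratory rate elsewhere in the SAP.** It does not appear in the readable text. The abbreviation RR in SAP 9.6.6 is in the list of ECG parameters and matches the RR interval in Protocol 9.2.3.3, so it is not respiratory rate.

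**Step 4: ask whether the omission comes from redaction or conversion.** The sentence in 9.6.4 is complete, with no redaction mark, and Appendix F repeats the same four parameters.

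**Step 5: ask whether the visit schedule explains it.** It does not, because one vital-signs row covers all the parameters. SAP 9.6.5 is a useful contrast: it restricts the physical measurements to a summary "of weight at scheduled time points" and omits height, but Protocol Table 2-1 schedules height only at screening, so there is nothing to follow over time. Respiratory rate has no such explanation.

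**Step 6: ask whether another planned output gives the same information.**
- Adverse-event tables (SAP 9.6.2): under Protocol Appendix 4, an abnormal vital sign becomes an adverse event when the investigator judges it clinically significant. That does not describe the measured values by group.
- Dose level review output (SAP 7.1): vital signs are to be listed or plotted for these meetings, with the full list of outputs in a separate plan that is not available here. SAP 9.1 keeps only critical subject-level listings in the study report and leaves out the additional ones reviewed at these meetings. It does not say which class vital signs fall in.

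Neither is a planned by-group summary of respiratory rate.

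**The case against.** The strongest reply is that nothing is contradicted. Protocol 9.2.3.2 governs measurement. The protocol's analysis section names no parameters, and both documents allow selection; SAP 9.1 has "Descriptive statistics will be provided for selected demographics, safety, PK, PD, and biomarker data". Narrowing general protocol text is part of a SAP's job, and 9.6.4 does so openly with a list. No respiratory-rate summary was specified in the protocol, so no entry in SAP Section 10 was strictly owed. The SAP also selects laboratory parameters for shift tables without giving reasons.

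In addition, the endpoint concerns clinically significant changes. Those reach the adverse-event tables, whereas means and extremes would not identify them, because the plan sets no threshold. The dose level review members see vital-sign data in any case.

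Most of this stands as a limit on severity. No explicit promise is broken, safety oversight is not shown to lose anything, and it would go too far to say that the study report will contain nothing on respiratory rate. What does not follow is that the omission is harmless as drafted. A general allowance for selection neither names respiratory rate nor explains dropping it, and the SAP describes the measured values of the other four parameters even though they have the same adverse-event safety net.

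**Conclusion.** The point holds and is minor. One of the five vital-sign parameters that must be measured has no by-group summary specified in the phase 1b primary safety analysis, and the readable SAP gives no reason. The effect is confined to descriptive reporting: no sample size, power, stopping rule or dose decision rule changes.

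The conclusion rests on two readings. The first is that the list in SAP 9.6.4 is meant to be exhaustive, which its wording supports. The second is that no redacted passage restores respiratory rate. The separate plan for the dose level review meetings could provide listings or plots of it, but that would not supply a treatment-group summary under this SAP.

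**What to change.** In SAP 9.6.4, add respiratory rate to the parameter list so that it receives the same three kinds of summary, by treatment group, as blood pressure, heart rate and temperature. The Appendix E visit windows for vitals are not limited to particular parameters, so they need no change.

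The cost is one more parameter in a table that is already planned. Protocol 9.2.3.2 already requires the values on the case report form, so no new data collection, visits or subjects are needed, and no protocol amendment is required.

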9.6.5 Physical Measurements

Phase 1b

The analyses of physical measurements will include summary statistics **of weight at scheduled time points** by treatment group.

9.6.6 Electrocardiogram

Phase 1b

Summaries over time and/or changes from baseline over time will be provided for all ECG parameters (PR, QRS, QTcF, QTcB, RR). Subjects' maximum change from baseline in QTcF, **and** QTcB will be categorized and the number and percentage of subjects in each group will be summarized. Subjects' maximum post baseline values will also be categorized and the number and percentage of subjects in each group will be summarized.

9.6.7 Antibody Formation

Phase 1b [REDACTED]

The incidence and percentage of subjects who develop anti-AMG 592 antibodies (binding and if positive, neutralizing) at any time will be tabulated by **treatment group**. The incidence and percentage of subjects who develop anti-AMG 592 antibodies that cross-react to IL-2 and who develop anti-IL2 neutralizing antibodies will also be tabulated

9.6.8 Exposure to Investigational Product

Phase 1b [REDACTED]

Descriptive statistics will be produced to describe the exposure to investigational product by treatment group.

The number of days on investigational product, **and** the cumulative total dose of investigational product will be summarized **for each treatment group**. Subject-level data may be provided instead of the summary if the subject incidence is low or single dose is given.

A listing of the unique manufacturing lot numbers, and a listing of the subjects administered each manufacturing lot number will be provided.

9.6.9 Exposure to Concomitant Medication

Phase 1b [REDACTED]

Number and proportion of subjects receiving concomitant medication for RA indication will be summarized by preferred term or category as coded by the World Health Organization Drug (WHODRUG) dictionary by treatment group.

9.7 Other Analyses

9.7.1 Analyses of Pharmacokinetic or Pharmacokinetic/Pharmacodynamic Endpoints

[figure not shown]
9.7.1.1 Analysis of Pharmacokinetic Endpoint

[figure not shown]
Phase 1b [REDACTED]

The Pharmacokinetic Concentration Analysis set defined in [Section 6](#) will be used in analyzing PK concentration data and the Pharmacokinetic Parameter Analysis Set will be used in analyzing PK parameters. Plasma concentrations of AMG 592 will be expressed in ng/mL. All concentrations below the limit of quantification or missing data will be labeled as such in the concentration data listings. Concentrations below the lower limit of quantification will be treated as zero in summary statistics.

Nominal sampling times will be used for individual concentration-time plots and tables. Actual dose administered, and actual sampling times will be used for the calculation of PK parameters for each subject. The reasons for excluding any sample from the analyses will be provided.

[figure not shown]
Individual concentration-time data will be tabulated and presented graphically. Summary of PK concentration over time and PK parameters will be provided. Mean concentration-time profiles for each dose will be provided. PK parameters will be summarized for each dose using descriptive statistics, including, but not limited to mean, standard deviation, CV, median and range. Analyses will be conducted by Amgen Clinical Pharmacology Modeling and Simulation (CPMS).

9.7.3 Analyses of Health Economic Endpoints

Not applicable for the study

10. Changes from Protocol-specified Analyses

ECG listing as planned in the protocol will not be provided because only critical data listings will be included in the CSR and summary tables planned for ECG data will be adequate to identify significant changes (if any) in ECG data.

11. Literature Citations / References

12. Prioritization of Analyses

There is no prioritization of analyses.

13. Data Not Covered by This Plan

Exploratory data not included in this plan may be analyzed at a later date or may be analyzed by a different Amgen Department.

14. Appendices

Appendix A. Technical Detail and Supplemental Information Regarding Statistical Procedures and Programs

Imputation Rules for Partial or Missing Stop Dates

If the month and year are present, impute the last day of the month. If only the year is present, impute December 31 of that year. If the stop date is entirely missing, assume the event or medication is ongoing and do not impute.

Imputation Rules for Partial or Missing Start Dates

		Stop Date							
		Complete: yyyymmdd		Partial: yyyymm		Partial: yyyy		Missing	
Start Date		<1 st Dose	≥1 st Dose	<1 st Dose yyyymm	≥1 st Dose yyyymm	<1 st Dose yyyy	≥1 st Dose yyyy		
Partial: yyyymm	=1 st Dose yyyymm	2	1	2	1	N/A	1	1	
	≠ 1 st Dose yyyymm		2		2	2	2	2	
Partial: YYYY	=1 st Dose yyyy	3	1	3	1	N/A	1	1	
	≠ 1 st Dose yyyy		3		3	3	3	3	
Missing		4	1	4	1	4	1	1	

[figure not shown]
1 = Impute the date of first dose

[figure not shown]
2 = Impute the first day of the month

[figure not shown]
3 = Impute January 1 of the year

[figure not shown]
4 = Impute January 1 of the stop year

[figure not shown]
For subjects who were never treated (first dose date is missing), partial start dates will be set to the first day of the partial month. If the start date imputation leads to a start date that is after the stop date, then do not impute the start date.

[figure not shown]

Appendix C. Reference Values/Toxicity Grades

The Common Terminology Criteria for Adverse Events (CTCAE) version 4.0 will be used and is available at the following location

http://ctep.cancer.gov/protocolDevelopment/electronic_applications/ctc.htm

Appendix E. Analytical Windows

The last visit with non-missing assessment prior to first dose will be defined as a baseline visit and the analysis visit name will be “Baseline”. For any visit up to Day 1 pre-dose which is not a baseline visit, the analysis visit will be ‘Pre-Analysis’. For post-dose assessments on Day 1 and assessments at Safety follow-up/EOS visit, the analysis visit will be same as the scheduled visit. Only for phase 1b, for post-dose assessments on Day 85 (the day corresponding to week 12 dosing), the analysis visit will be same as the scheduled visit. Remaining visits (scheduled or unscheduled) after Day 1 for any assessment will be mapped to the analysis visit based on visit windows defined in the tables below for that assessment. Only visits applicable for that assessment and phase of the study will be considered for analysis.

Data collected through central lab and local lab will both be mapped into analysis visit windows. The local lab data can only be used in analysis when there is no central lab data available in the analysis visit window.

If more than one visit with non-missing data falls within an analysis visit window, the visit closest to the target day will be considered for analysis. If two visits are equidistant from the target day, the latest visit (or time if on the same day) will be considered. If more than one evaluation has same date and time (for chemistry, hematology or pharmacodynamic results), the value with the smallest accession number will be considered.

Analysis visit windows for selected assessments are included in tables below. For remaining assessments, no visit window will be applied. Day 85 used in Study day window calculation in the tables below is the study day when Week 12 dose was received. If that dose is missing, then 85 is used for calculation.

Phase 1b

Vitals

Analysis Visit	Target Day	Study Day Window
Week 1, Day 2	2	2
Week 1, Day 3	3	3
Week 1, Day 4	4	4-6
Week 1, Day 8	8	7-9
Week 1, Day 11	11	10-12

Analysis Visit	Target Day	Study Day Window
Week n, Day 7*n+1 (n = 2, 3, 4, 5, 6, 7,8, 9, 10)	7n+1	Target day -2, Target day +4
Week 11, Day 78	78	76- (Day 85-3)
Week 12, Day 85 Pre-dose	85	Day 85-2, Day 85
Week 12, Day 86	86	Day 85 +1
Week 12, Day 87	87	Day 85 +2
Week 12, Day 88	88	Day 85 + 3
Week 13, Day 92	92	(Day 85 + 4) -96
Week 14, Day 99	99	97-106
Week 16, Day 113	113	>106

Chemistry, hematology, weight, and ECG (Phase 1b only)

Analysis Visit	Target Day	Study Day Window
Week 1, Day 2	2	2-3
Week 1, Day 8	8	4-12
Week 2, Day 15	15	13-22
Week n, Day 7*n+1 (n = 4, 6, 8)	7*n+1	Target day -6, Target day +7
Week 10, Day 71	71	65- (Day 85-7)
Week 12, Day 85	85	Day 85-6, Day 85 +7
Week 14, Day 99	99	(Day 85+8)-106
Week 16, Day 113	113	> 106

Antibody assessments, [REDACTED]

Analysis Visit	Target Day	Study Day Window
Week 2, Day 15	15	2-22
Week 4, Day 29	29	23-43
Week 8, Day 57	57	44- (Day 85 -14)
Week 12, Day 85	85	Day 85- 13, Day 85 +7
Week 14, Day 99	99	> Day 85 + 7

Appendix F. Summary of changes and rationale for changes to the SAP Amendment 1

The statistical analysis plan for this study was amended to reflect the changes in recent protocol amendment 3. Editorial changes and minor clarifications were also implemented throughout the document.

Description of Changes

Global

- Header date was replaced with 7 February 2019.
- Header version number was replaced with Version 2.0.
- Removal of unnecessary listings as per recent process

